FV & FVIII deficiency

Combined FV & FVIII deficiency is an autosomal recessive disorder. Individuals with a FV and FVIII deficiency do not have a more severe bleeding tendency than individuals with either a FV or a FVIII deficiency [28]. Those affected usually have a mild to moderate bleeding tendency, with mucous membrane bleeding like epistaxis (19 to 77%), gum bleeding (49 to 64%), menorrhagia (66 to 100%) and post-traumatic/post-surgery (62 to 85%) as the most common manifestations [29]. Joint and muscle bleedings were reported in 25% and 7% of 27 patients in one series, but it was not reported whether these bleedings were spontaneous [23]. In the same patient series 22% reported cord bleeding and 4% central nervous system bleeding.

FVII deficiency

FVII deficiency is an autosomal recessive disorder. The clinical manifestation is heterogeneous. There is a weak correlation between the level of FVII and bleeding tendency. Mild disease will lead to easy bruising, bleeding from mucous membranes or menorrhagia [5]. Severe and homozygous FVII deficiency may lead to haemarthrosis, cerebral haemorrhage and catastrophic haemorrhage after parturition, surgery or injury [5, 30]. In a large series of 73 homozygous individuals intracranial haemorrhage (2%), gastrointestinal bleeding (17%), haemarthrosis (13%), epistaxis (58%), gum bleeding (38%), easy bruising (37%), haematoma (15%), hematuria (10%) and menorrhagia (73%) were described [31]. Interestingly, 19% of heterozygous individuals reported spontaneous bleeding, though severe spontaneous haemorrhages (intracranial and gastrointestinal) were not reported in this series [31]. In contrast, in a series of 49 patients with <10% FVII 17% reported central nervous system bleeding and 14% gastrointestinal bleeding [23].

FX deficiency

FX deficiency is an autosomal recessive disorder. The risk of bleeding correlates well with coagulation factor activity level [19]. Severe bleeding occurs in patients with factor levels below 10%, and includes umbilical cord, intracranial, joint and muscle bleeding and excessive bleeding after surgery or trauma. Heterozygous individuals can have a bleeding tendency. [32].

FXI deficiency

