FXI deficiency can be inherited autosomal recessive and autosomal dominant[33]. It is the mildest of the rare bleeding disorders, with bruising, epistaxis and menorrhagia as the most common manifestations [5, 14]. The correlation between coagulation factor activity and clinical bleeding is poor [19]. This may (in part) be explained by the coexistence of other coagulation disorders. In some patients with severe FXI deficiency a combined FXI and von Willebrand disease has been reported, leading to a more severe bleeding tendency [16]. Excessive bleeding has also been reported in heterozygous individuals. A single study from the United Kingdom showed that 48% of heterozygous individuals had a bleeding tendency, [34]. Comparison of histories between partially deficient and non-deficient individuals demonstrated a higher prevalence of menstrual problems (41% vs. 18%), an increase in significant bruising (38% vs. 14%), an increased likelihood of excessive bleeding after dental extractions (51% vs. 9%), and an increased number of blood transfusions after interventions (56% vs. 0%). Bleeding in heterozygous individuals has also been described to be related to genetically compound disease, other factor deficiencies or defects, or platelet dysfunction in some cases [12-18].

FXIII deficiency

FXIII deficiency is an autosomal recessive disorder. This deficiency has serious clinical consequences. Of 112 cases reported in the literature from 1978 23 individuals (21%) had died of bleeding, and notably 22 of these were relatives of established cases, for whom the diagnosis was highly likely but could not be proven [35]. Umbilical cord bleeding was seen in

73-80% of cases and may be delayed up to 19 days after birth; surgical bleeding in 84%; superficial bruising in 58-60%; subcutaneous haematomas in 55-58%; intracranial bleeding in 25-30%; mouth and gum bleeding 30-48%; muscle bleeding 27%; and joint bleeding in 24-55% of reported cases [35, 36]. Habitual abortions (50% of women) and menorrhagia (35% of women) are also frequent. Women with a complete deficiency are unable to carry a pregnancy to term [36, 37]. Impaired wound healing is another symptom patients may experience [37]. It is currently not clear if people with a heterozygous factor XIII deficiency have an increased bleeding risk[38].

Alpha-2-antiplasmin deficiency

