5.3. Exclusion criteria

A potential subject who meets any of the following criteria will be excluded from participation in this study:

- No informed consent given;
- Residency outside of the Netherlands

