In adults and children ≥ 12 years old, roughly 67 ml blood will be drawn through a study-related venepuncture. Forty-seven ml of this sample will be used for this study while the remaining 20 ml will be stored in the Radboud university medical center Biobank for future research. Additional information about the Biobank is provided in separate documents.

Blood samples will be used for the experiments specified in table 4.

In children under 16 years of age, whole exome sequencing will not be performed. Also, the following tests are not performed under 12 years of age: ALAT, TSH, creatinine, lupus anticoagulans and d-dimer. Therefore, only 47mL of blood will be needed for these children. For children under 8 years of age, in addition there will be no blood drawn for the biobank so that they only need to supply 27mL of blood.

Remaining material can be used for future research. In this case, studies will be performed according to the protocol Biobank Hematologie HEMBB (IRB Registration number: CMO Arnhem-Nijmegen 2013/064). In case the research would not be within the scope of HEMBB, the CMO will be consulted in advance.

Saliva sampling

Whole saliva will be collected in the morning when patients did not drink more than 2 glasses of alcohol on the evening before and did not eat 1 hour before collection. In case of infections

in the oral cavity or a severe cold, patients will be excluded. Before saliva collection the mouth will be rinsed with water and donors will be allowed to chew on 25 cm² sheet of parafilm (Parafilm® M) for 1 minute. Produced saliva will be collected into a 50 ml tube and centrifuged at 10,000g for 10 minutes. Samples will be divided in aliquots of 250 µl and stored at -80°C. Stimulated whole saliva collection will be used because of its non-invasive approach instead of e.g. glandular saliva donation, and since stimulated whole saliva has been found to have a large portion of peptides and proteins derived from the parotid glands. Specimens will be processed with several techniques including ELISA and proteomics.

Saliva samples are only collected in patients ≥4 years old.

Electronic patient records

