7.2. Secondary objectives

- *Compare the clinical presentation, bleeding score, quality of life and laboratory parameters of individuals with a rare bleeding disorder (disorders of fibrinogen, FII, FV, FV & VIII, FVII, FX, FXI, FXIII and alpha-2-antiplasmin and PAI-1 deficiency) to those of individuals with haemophilia A or B (HiN study data will be shared)*
Descriptive statistics will be used. Group differences will be determined using the statistics as described in Statistical Analysis above.
- *Establish a firm base for a future Dutch registry for homozygous and known heterozygous individuals with rare bleeding disorders (disorders of fibrinogen, FII, FV, FV & FVIII, FVII, FX, FXI, d FXIII and alpha-2-antiplasmin and PAI-1 deficiency):*
 - *To develop a standard set of patient-reported, clinical and administrative data to be collected on a regular basis*

No statistics are involved in this objective.

- *Liaise with the pro-RBDD study, a similar study in Italy, to work towards a pan-European study linking phenotype to genotype in individuals with rare bleeding disorders*
No statistics are involved in this objective.
- *To assess if the NHA can distinguish mild clinical phenotypes in patients with similar factor activity levels*
We will calculate diagnostic accuracy comparing NHA to ISTH BAT.
- *To evaluate the usefulness of saliva coagulation biomarker tests in the management of patients with a rare bleeding disorder*
Descriptive statistics will be used. Regression analysis will be used to determine the association between saliva biomarker tests (dependent variable) and coagulation factor activity level as a continuous variable (independent variable), with adjustment for age at data collection, sex, etcetera.

- *To evaluate the use of WES in explaining differences in bleeding tendency.*
Descriptive statistics will be used.
- *To examine whether age-dependent laboratory changes in factor concentrations and fibrinolysis occur individuals with rare bleeding disorders? And if so, do they influence clinical phenotype?*
Descriptive statistics will be used. Regression analysis will be used to determine the association between age (dependent variable) and coagulation factor activity level as a continuous variable (independent variable), with adjustment for age at data collection, sex, etcetera.
- *To evaluate if patients with rare bleeding disorders are protected from arterial thrombosis*

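### The saliva rule screens for oral infection and severe cold but not for oral bleeding, so blood in some samples could distort the saliva biomarker associations, by an amount the documents do not allow one to estimate

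*Combined protocol and SAP*

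**What the plan says.** Section 6.2 (Saliva sampling) sets conditions on time of day, alcohol the evening before, and food: the patient "did not eat 1 hour before collection". For infections "in the oral cavity or a severe cold, patients will be excluded". Handling is then described: "Before saliva collection the mouth will be rinsed with water", the participant chews parafilm for one minute, and the saliva is "collected into a 50 ml tube and centrifuged at 10,000g for 10 minutes". Whole stimulated saliva is used, from age 4, and goes to ELISA and proteomics. Oral bleeding, visible blood and contamination markers are not mentioned here or elsewhere in the protocol.

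Section 1.2 describes oral bleeding in several of the included disorders: "gum bleeding (49 to 64" per cent in combined FV & FVIII deficiency, "mouth and gum bleeding 30-48" per cent in FXIII deficiency, and 38% gum bleeding among 73 homozygous FVII patients. Section 7 counts oral cavity bleeding and epistaxis as Grade II bleeding.

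For the analysis, section 7.2 states: "Regression analysis will be used to determine the association between saliva biomarker tests (dependent variable) and coagulation factor activity level". The named covariates are age and sex, followed by an open-ended etcetera. Section 2 also intends to relate the saliva biomarkers to clinical phenotype and, if they correlate, to ask whether they could support monitoring and treatment decisions.

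The study-level exclusions in section 5.3 are absence of consent and "Residency outside of the Netherlands".

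**The concern.** The analytes are biomarkers of coagulation, and blood in the mouth carries plasma coagulation proteins. The protocol accepts that the state of the mouth can spoil the sample, since it screens for infection, but it leaves out the condition closest to the diseases under study. Oral bleeding is also part of the clinical severity scale, so contamination need not be neutral noise: it may be more frequent in patients with lower factor levels or worse phenotype. An association could then reflect leaked blood rather than a salivary signal, or a real signal could be blurred. The Summary describes a single visit and section 6.5 states that there is no follow-up, so blood that is not noted at collection cannot be noted later.

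A smaller wording point sits in the same sentence: it speaks of excluding patients, without saying that only the saliva sample is meant.

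**Working it through.** The plan gives no sample size, power or effect size for the saliva objective, so there is no figure of its own to reproduce. The check has three steps.

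1. **What the collection steps control.** The rinse can clear blood already in the mouth, but it comes before the chewing that may provoke gum bleeding. By general laboratory reasoning, centrifugation at 10,000g pellets cells but leaves soluble plasma proteins in the supernatant. Screening for infection may remove some gum disease, but does not address bleeding from a coagulation defect. These are partial controls.

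2. **How far the bleeding histories reach.** Table 3 counts sum to the stated 337. Applying the section 1.2 percentages to every known patient in those disorders:
 - FVII: 92 × 0.38 = 35.0
 - FXIII: 16 × 0.30 to 16 × 0.48 = 4.8 to 7.7
 - FV & FVIII: 4 × 0.49 to 4 × 0.64 = 2.0 to 2.6
 - Sum: 41.7 to 45.2 of 337, or 12-13%

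 Adding the hypofibrinogenemia series (70%, but mouth and nose combined) gives 28 × 0.70 = 19.6 more, so 61.3 to 64.8, or 18-19%. If the percentages hold only for a homozygous third, divide by 3: about 4% without and 6% with fibrinogen. No gum or mouth percentage is given for the other 337 − 140 = 197 patients, who are counted as zero here. All of these are histories, not bleeding at sampling.

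3. **When contamination biases the regression.** Illustrative model, with no true salivary signal: factor level x is uniform on 0-1; the biomarker is y = e + d·b, where e has SD 1, b marks blood in the sample, and d is the shift in SDs. Blood is present with probability p_L in the lowest third of x and p_H elsewhere, so overall p = (p_L + 2p_H)/3. Then

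 cov(x, b) = −(p_L − p_H)/9

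 corr(x, y) = −d(p_L − p_H)/9 ÷ [√(1/12) × √(1 + d²p(1 − p))]

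 This is zero when p_L = p_H. With p_L = 0.20, p_H = 0.05, d = 3: p = 0.10, and the correlation is −0.05 ÷ (0.2887 × √1.81) = −0.13.

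 Simulated false-positive rates at two-sided 0.05 (n = 0.70 × 337 = 236; 4,000 replicates; no covariates):

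| Blood in sample: lowest third vs rest | d = 1 | d = 2 | d = 3 |
|---|---|---|---|
| 5% vs 5% | 5.0% | 5.1% | 4.5% |
| 5% vs 2% | 5.6% | 6.6% | 7.7% |
| 10% vs 2% | 7.9% | 14.1% | 23.0% |
| 15% vs 5% | 9.0% | 18.4% | 28.7% |
| 20% vs 5% | 13.8% | 32.5% | 50.0% |
| 30% vs 5% | 29.3% | 68.1% | 87.4% |

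 The contamination rates and shifts are assumptions; none comes from the documents. Even equal contamination has a cost: at 5% and d = 3 the biomarker SD becomes √(1 + 9 × 0.05 × 0.95) = 1.19, which shrinks a true correlation to about 1/1.19 = 0.84 of its value.

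**The case against.** Four arguments deserve weight.

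- **Oral bleeding may be infrequent in this cohort.** The highest percentage belongs to a disorder with 4 known patients, and the FVII figure comes from homozygous patients, while about two thirds of known Dutch patients are thought to be heterozygous. FXI (88 patients), PAI-1 (39) and alpha-2-antiplasmin (29) have no gum-bleeding percentage. Section 1.2 itself warns that published series may overstate severity. This stands: gum bleeding is documented as frequent in several disorders, not across the study population.
- **The bias needs contamination to vary with factor level.** The protocol calls the link between factor level and bleeding weak or absent for FV, FVII and FXI: 22 + 92 + 88 = 202 of 337 patients (60%). This stands for the specified regression. It bears less on the clinical-phenotype correlation announced in section 2, for which section 7.2 specifies no saliva model.
- **Safeguards exist.** The rinse and centrifugation count, but only in part, as shown in the working.
- **Excluding samples by bleeding would itself select on phenotype.** This stands, and it is why the main analysis should keep every sample.

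A reader might go further and infer that the saliva tests will merely measure blood in the mouth, or that a given number of samples will be spoiled. The documents support neither: they name no biomarkers, give no rate of bleeding at sampling, and rest the method on unpublished data. Nor do they support the inference that a patient with a cold would be dropped from the whole study. The sentence stands under Saliva sampling, section 5.3 lists no such criterion, and all known patients are to be invited.

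**Conclusion.** The gap is real and the point holds with limits. The stated rule would admit blood-contaminated saliva without any trace of it in the data, and nothing else in the protocol closes the gap. Distortion is possible where contamination varies with factor level or phenotype. Its size is unknown: under the assumptions shown, the false-positive rate ranges from no inflation to severe inflation. One exploratory secondary objective is affected and no primary objective. The conclusion assumes that no separate saliva working instruction, outside the supplied documents, already covers blood in the sample. The exclusion wording is a minor clarification.

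**What to change.** - At collection, record in the eCRF (a) visible blood in the saliva sample and (b) current or recent oral or nasal bleeding. The investigators should define recent, since the documents offer no window.
- Where the planned ELISA or proteomics work allows, include a marker of blood contamination.
- Keep all samples in the main saliva regression. Pre-specify a sensitivity analysis that excludes visibly blood-stained samples or adjusts for the marker, and interpret a saliva association as useful only if it persists.
- Reword the exclusion sentence to the effect that, with an oral infection or severe cold, only the saliva sample is omitted and all other study procedures go ahead.

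The cost is two eCRF items, possibly one extra analyte, one extra analysis and one reworded sentence. No samples are discarded from the main analysis and no second visit is needed.

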6.3. Withdrawal of individual subjects

Subjects can leave the study at any time for any reason if they wish to do so without any consequences. The investigator can decide to withdraw a subject from the study for urgent medical reasons.

6.4. Replacement of individual subjects after withdrawal

Not applicable as all known patients will be invited to participate.

6.5. Follow-up of subjects withdrawn from treatment

Not applicable as this study has no follow-up.

6.6. Premature termination of the study

If the recruitment of subjects goes unexpectedly too slow within a reasonable time period the study ends prematurely. Too slow a recruitment is defined as less than one fifth of known patients, thus, less than 60 patients, within one year of the start of the study.

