1.5. Genetics

In general, mutations in genes that encode for the corresponding coagulation factor are the cause of the bleeding disorder, and mutations are almost always unique to single kindred (Table 2). The combined deficiency of FV & FVIII is caused by mutations in genes encoding for proteins involved in intracellular transport [41]. Deficiencies in the vitamin K dependent coagulation proteins (FII, FVII, FIX and FX) can be caused by mutations in genes encoding enzymes involved in post-translational modification and in vitamin K metabolism [42].

In approximately 10% to 20% of patients, no putative mutation is found with conventional genetic techniques that scan the 'usual suspect' genes. Cases where no putative mutation has been found may be due to defects in non-coding regions or in genes coding for regulators of intracellular transport and posttranslational modifications of coagulation factors.

Table 2 General genetic features of the rare bleeding disorders [10, 23]

Disorder factor	Gene on chromosome
Fibrinogen	4
II	11
V	1
V & VIII	18

VII	13
X	13
XI	4
XIII	A subunit: 6 B subunit: 1
PAI-1	7
Alpha-2-antiplasmin	17

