5. STUDY POPULATION

5.1. Population (base)

Based on the prevalence in the general population of 1:500,000 to 1 per 2 million persons [1, 2], and a total population of 17 million, there should be 129 to 145 individuals with a homozygous rare bleeding disorder in the Netherlands. This could be higher taking into account the possible influences of high-risk populations such as Ashkenazi or Iraqi Jews with high FXI deficiency rates. To date, 337 patients with a rare bleeding disorder are known to the eight Dutch centers that treat such patients. Approximately one third of these patients are homozygous; and around two thirds are heterozygous individuals.¹

All known homozygous and heterozygous patients with a rare bleeding disorder will be invited to participate.

Heterozygous prevalence in the Netherlands have not been evaluated, but can be calculated according to the Hardy-Weinberg principle² to be 93,000 to 99,000 persons, or 0.55% to 0.58% of the Dutch population (5.5 to 5.8 per 1,000 persons) for all rare bleeding disorders combined. Though the estimated number of heterozygous persons in the Netherlands is much higher than the number of persons known to one of the eight treating centers (~179 heterozygous patients³), we expect that the individuals with a known heterozygosity represent a subset with a more severe clinical presentation, who are therefore of interest to our research question.

Characteristics of the Dutch source population

The characteristics of the Dutch population (both homozygous and heterozygous) are largely unknown and are a part of this study. Numbers of known patients per rare bleeding disorder are presented in

[Table 3](#)

[Table 3.](#)

¹ A quick inventory in the Radboud university medical center learned that two thirds of patients were heterozygous individuals whereas one third were homozygous individuals. Based on an inventory of 63 medical files performed on July 8, 2016: 65% missing information, 24% heterozygosity, 11% homozygosity

² The Hardy-Weinberg proportion stipulates that for a single locus with two alleles denoted 'A' and 'a' with population frequencies p and q respectively, the expected genotype frequencies are p² for the AA homozygous individuals, q² for the aa homozygous individuals, and 2pq for the heterozygous individuals. The sum of these frequencies must be 1, thus p² + 2pq + q² = 1 and p + q=1.

Table 3 Prevalence of rare bleeding disorders in the Netherlands

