Deficiency	Estimated prevalence homozygosity in general population as described in the literature [1, 2]	Estimated prevalence homozygosity in the Dutch general population	Patients known at present in the Netherlands (homozygous/heterozygous/unknown)
Fibrinogen	1:1 million	17	28
II	1:2 million	9	9
V	1:1 million	17	22
V & VIII	1:1-2 million	9-17	4
VII	1:500,000	34	92
X	1:1 million	17	10
XI	1:1 million	17	88
XIII	1:1-2 million	9-17	16
PAI-1	Unknown	Unknown	39
Alpha-2-antiplasmin	Unknown	Unknown	29
	Total	129-145	337

Abbreviations: CI: confidence interval

\$ Based on a population figure of 17,024,133 (www.cbs.nl/nl-nl/visualisaties/bevolkingsteller)

* Based on a quick inventory of participating sites, which are all sites in the Netherlands licensed to treat rare bleeding disorders. Homozygosity or heterozygosity largely unknown

Willingness of patients to participate

We expect that a high proportion of patients with rare bleeding disorders are willing to participate in RBiN. Patients are aware of the rarity of their disorder and the lack of research. The Netherlands Hemophilia Society (Nederlandse Vereniging van Hemofilie Patiënten, NVHP) is a co-initiator of RBiN and a patient representative takes seat in the steering committee. Based on the response rate of the HiN studies we expect a (similar) response rate of 70% [51].

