9.5. Temporary halt and (prematurely) end of study report

The investigator/sponsor will notify the accredited METC of the end of the study within a period of 8 weeks. The end of the study is defined as the last patient's last visit.

The sponsor will notify the METC immediately of a temporary halt of the study, including the reason of such an action.

In case the study is ended prematurely, the sponsor will notify the accredited METC within 15 days, including the reasons for the premature termination.

Within one year after the end of the study, the investigator/sponsor will submit a final study report with the results of the study, including any publications/abstracts of the study, to the accredited METC.

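### The early-termination rule in 6.6 gives two thresholds: one fifth of the 337 known patients is 67.4, not 60, so 60 to 67 recruits lead to opposite decisions

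*Combined protocol and SAP*

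**What the plan says.** Section 6.6 sets a recruitment floor, below which the study ends: "Too slow a recruitment is defined as less than one fifth of known patients, thus, less than 60 patients, within one year" of the start.

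The base for that fraction is in section 5.1: "To date, 337 patients with a rare bleeding disorder are known to the eight Dutch centers". Table 3 gives the same total. All known patients, homozygous and heterozygous, are to be invited. On participation, 5.1 states: "we expect a (similar) response rate of 70" per cent.

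An early end has a reporting consequence in section 9.5: "In case the study is ended prematurely, the sponsor will notify the accredited METC within 15 days", with reasons.

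Section 5.1 also estimates the number of heterozygotes in the Netherlands, for all the disorders together, "to be 93,000 to 99,000 persons, or 0.55% to 0.58% of the Dutch population". The formula is in footnote 2: "The Hardy-Weinberg proportion stipulates that for a single locus with two alleles". Section 1.5 says that, in general, "mutations in genes that encode for the corresponding coagulation factor are the cause of the bleeding disorder", and Table 2 lists the gene locations by disorder.

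**The concern.** The wording of 6.6 presents 60 as the result of taking one fifth of the known patients. It is not one fifth of the only total the protocol gives, so the rule contains two different thresholds. Where recruitment falls between them, both stopping and continuing can be defended from the same sentence, and either can be faulted. A termination rule should give one answer, settled before the recruitment count is seen.

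The second point is background. The heterozygote estimate appears to add the expected homozygotes over disorders first and then apply a formula for one locus. Carrier frequency depends on the square root of homozygote frequency, so pooling before taking the root gives too low a figure. This touches no sample size, test or recruitment target.

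**Working it through.** **Termination threshold**

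Inputs: known patients by disorder (Table 3), the fraction and the number (6.6), the expected response (5.1).

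- Total known: 28 + 9 + 22 + 4 + 92 + 10 + 88 + 16 + 39 + 29 = 337, which agrees with the text of 5.1.
- One fifth: 337 / 5 = 67.4. Below one fifth therefore means 67 or fewer (67/337 = 19.9%; 68/337 = 20.2%).
- The stated number: 60/337 = 17.8%. It lies 7.4 patients, or 7.4/67.4 = 11%, below the stated fraction.
- Counts at which the two wordings disagree: 60, 61, 62, 63, 64, 65, 66 and 67.

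The stated 60 would need a base of 60 × 5 = 300, which appears nowhere. Other bases that can be formed from the protocol:

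| Base | Patients | One fifth |
|---|---|---|
| All known patients | 337 | 67.4 |
| Expected responders, 0.70 × 337 | 235.9 | 47.2 |
| Eight disorders with a stated prevalence | 269 | 53.8 |
| Known heterozygotes | about 179 | 35.8 |
| Table 3 without PAI-1 | 298 | 59.6 |
| Table 3 without alpha-2-antiplasmin | 308 | 61.6 |

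Only the last two come near 60. Neither is the protocol's population, because both disorders are in the objectives, the inclusion criteria and Table 3.

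**Heterozygote estimate**

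Inputs: N = 17,024,133 and the prevalences in Table 3; 129 to 145 expected homozygotes (5.1). Formula: q = √(homozygote frequency), carriers = 2q(1 − q)N.

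First, the plan's own figure, with all disorders treated as one locus:

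- 129 homozygotes: 2q(1 − q) = 0.549%, or 93,467 persons.
- 145 homozygotes: 2q(1 − q) = 0.582%, or 99,078 persons.

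This reproduces the stated range and shows that the disorders were pooled.

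Then per disorder:

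- 1:2 million: 0.001413, or 24,059 carriers.
- 1:1 million: 0.001998, or 34,014 carriers.
- 1:500,000: 0.002824, or 48,083 carriers.

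At the low end, four disorders are at 1:1 million (fibrinogen, V, X, XI), three at 1:2 million (II, V & VIII, XIII) and one at 1:500,000 (VII). The sum is 0.015056, or 256,317 carrier states. At the high end, V & VIII and XIII move to 1:1 million. The sum is 0.016226, or 276,227 carrier states.

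Persons with at least one carrier state, 1 − Π(1 − hᵢ) with hᵢ the carrier frequency of disorder i and independence assumed: 1.496% to 1.611%, or 254,648 to 274,283.

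Ratio to the pooled figures: 254,648/93,467 = 2.72 and 274,283/99,078 = 2.77 for persons; 2.74 and 2.79 for carrier states. With the higher FX prevalence in Table 1 (1:500,000), the upper end becomes about 290,000 carrier states, or 288,000 persons.

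**The case against.** The arithmetic is not in dispute; the weight is. This is a cross-sectional observational study. The threshold affects no estimate, error rate or analysis, and it conflicts only if one-year recruitment lands on one of eight counts, against about 236 expected. The duty to notify the METC applies to any early end, whichever threshold is used. All of this stands, and it makes the impact modest. It does not make the sentence consistent.

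One could read 60 as the operative number and the fraction as a loose description. The sentence works against this, because it derives the number from the fraction, and 67.4 does not round to 60.

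The number may be left over from an earlier patient count. Without PAI-1, one fifth is 59.6. The roughly 179 known heterozygotes in 5.1 likewise equal two thirds of 269 (179.3), whereas two thirds of 337 is 224.7. This is plausible but inferred. It would explain the mismatch without removing it.

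The base is itself soft: 337 comes from a quick inventory of sites, and some known patients may be ineligible (under one year of age, or living abroad). That is a reason to say when the base is fixed.

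On heterozygotes, the replacement holds only if each disorder is one recessive locus. The protocol departs from this in several places. For example, section 1.2 says "FXI deficiency can be inherited autosomal recessive and autosomal dominant" and describes dominant fibrinogen disorders. Section 1.5 gives two genes for FXIII and attributes combined FV & FVIII deficiency to intracellular transport genes. The corrected figure is therefore an order of magnitude. The point is also separate from 6.6 and adds nothing to its importance.

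**Conclusion.** The concern holds. Section 6.6 is wrong as written: its fraction gives 67.4 and its number is 60, 11% lower, and the two give opposite decisions at 60 to 67 recruits. This rests only on 337 being the number of known patients, which the text of 5.1 and Table 3 both state. The practical risk is small, since it arises only if one-year recruitment is 17.8% to 19.9% of known patients. The documents do not show which threshold was intended.

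The heterozygote figure is also wrong by its own formula, by a factor of about 2.7 to 2.8, assuming one recessive locus per disorder, random mating and, for persons, independence between loci. It covers only the eight disorders with a stated prevalence, although 5.1 presents it as covering all of them. The correction strengthens the statement it supports, that carriers far outnumber the known heterozygotes, and changes no result.

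**What to change.** **Section 6.6.** State one threshold. Either:

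- fewer than one fifth of the 337 known patients, that is, fewer than 68, within one year of study start; or
- fewer than 60 patients (about 18% of the 337 known) within one year, with the mention of one fifth deleted.

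The sponsor must choose, and should say whether the base is fixed at 337 or recounted at a stated date. The first option is slightly stricter (68 instead of 60 patients needed to continue); the second keeps the present number. The cost is one sentence.

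**Section 5.1 (minor).** Compute 2pq for each disorder in Table 3 and then combine, giving about 255,000 to 274,000 persons (1.5% to 1.6%). Say that this covers the eight disorders with a known prevalence, assumes one recessive locus per disorder and random mating, and is an order of magnitude, given the dominant forms, the multiple genes and the high-risk populations for FXI that the protocol describes. The cost is one or two sentences. While 5.1 is open, check whether the count of about 179 known heterozygotes was derived from the current total of 337.
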